The study to be Carried out will be Explained and read and, where appropriate, the informed consent will be signed by the Patient During the initial visit (Visit 1) of eligibility, Where the subject will be Given 2 questionnaires (see annexes), one They meet to determine if the ROME III criteria for functional constipation (FC) and another to ASSESS if the patient does not meet the criteria for irritable ROME III bowel syndrome (IBS) and a baseline breath test will be performed.

Having met the inclusion criteria, the patient will be EVALUATED by a graduate in nutrition with the objective of Evaluating the fiber intake in the subject's usual diet. The amount of daily fiber intake will be standardized and a diary will be Given to Evaluate Said intake (see annexes) as well as a diary Where the subject will keep a record of his / her evacuations (see annexes).

In Addition, the previous use of fiber supplements and laxatives, which must be suspended at Least 2 months prior to randomization, will be EVALUATED.

The subject will return to a second visit (Visit 2) (Which will depend on Whether the patient is taking laxatives or fiber supplements) for a complete physical evaluation and the fiber intake diary will be Assessed to determine the amount of fiber intake in the diet as well as the diary of evacuations and the SmartPill © will be Given and That way, the patient will return to the hospital to register the data after the capsule Having evacuated.

The patient will return a week later (Visit 3) on a 12 hour fast, the fiber intake and the evacuation diaries will be re-EVALUATED and will be EVALUATED They again by a nutritionist. A new breath test will be Carried out. The subject will be

Asked to complete the SF-36 Quality of Life Questionnaire. A stool sample will be Collected for ITS analysis in Addition to a blood sample for determination of fasting glucose, glycosylated hemoglobin A1c, Insulin and full lipid profile.

The subjects will be randomized to receive one of four treatments That can be Psyllium plantago 15g, blue agave Tequilana Weber fructans at doses of 5, 10g and blue agave Tequilana Weber fructans at a dose of 5 g + 10 g excipient for a concentration of 33 % of blue agave fructans Tequilana Weber.

The randomization will be computer-generated with a participation number and the assignment of the treatment will be consecutive.

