effects on intestinal transit Have Been observed from the first week of intake, in fact this is one of the Reasons to focus the study on functional constipation and intestinal transit.

Breath test:

A breath test will be Carried out in order to measure hydrogen and methane Concentrations previousle Exhaled In Patients randomized in visits 1 and 5.

In order to carry out the breath test gas chromatography equipment will be used, brand Quintron Breath Tracker.

For That, The Patients will be Asked:

- Not to take antibiotics prior weeks At least to the test.
- Stop the intake of food rich in fibers and starches 24 h before the test.
- Not to take alcohol, or smoke
- Have a minimum of 8 hours fasting
- Perform oral hygiene before starting the test and during the performance of measurements.

This test lasts 3 hours, during which the patient can not leave the laboratory facilities motility, can not speak too much or sleep. Exhaled air samples are taken every 15 minutes during this period.

SmartPill®:

[figure not shown]
SmartPill® test will be conducted on visits 2 and 4.

colonoscopy:

Colonoscopy study is a tool which will be subject to scrutiny patients ≥ 55 years with newly diagnosed constipation or those where changes in bowel habits observed in this age group. This fundamental objective, rule out potentially serious diseases and not to delay the diagnosis of these during the research study. one colonoscopic study all patients who have constipation and any of the following characteristics will be used:

1. Diagnosis of constipation less than 1 year
2. Subjects ≥ 55 years who do not have colonoscopic evaluation in the last 3 years prior to study entry
3. Chronic but with alarm data (: Unexplained weight loss, recent transrectal bleeding < 6 months, recent changes in the defecation pattern example) Constipation

Study Flow Chart

Patients include:

Studies with fiber supplements (Psyllium, Plums⁸) Have included 25 to 30 patients per group to find differences between groups.

In total it is planned to include 60 patients randomized as follows: 15 patients receive fructans blue agave Tequilana Weber dose of 5 g, 15 patients received the dose of 10 g, 15 patients received the dose of 5g of agave fructans blue Tequilana Weber + 10 g excipient and 15 patients received 15 g plantago psyllium.

9. Methodology Selection Criteria

a) Inclusion criteria (consider not participating in other research and contraception if necessary)

- Patients over 18 years old.

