- functional constipation ROME III criteria as
- Subjects ≥55 years with recent colonoscopy (<3 years)

b) Exclusion criteria

- Taking supplements of fiber in the last 2 months
- Stimulant laxatives consumption chronically (Senna, Bisacodyl)
- decompensated comorbidities (example: uncontrolled diabetes mellitus HbA1c > 9%, decompensated Organ failure, decompensated hypertension (untreated or TA > 160 mmHg systolic and 95 mmHg diastolic)

- Using digital maneuvers or enemas to achieve evacuation
- Personal history of active or previous cancer
- abdominal surgery (except appendectomy, cholecystectomy, hysterectomy)
- Presence of alarm data in the last 6 months (trans-rectal bleeding, unexplained weight loss, abdominal pain)
- Use of drugs known promote constipation (opioid derivatives, clacioantagonistas, anticholinergics tricyclic antidepressants type)
- Prostration (immobility or poor mobility)
- Diseases such as untreated hypothyroidism with hormone replacement, and diseases associated with hypercalcemia that promote constipation
- Other causes of secondary constipation
- Meet criteria for constipation predominant irritable bowel
- Pregnancy.

c) Elimination criteria (considering pregnancy if necessary).

- Requiring individuals to withdraw their informed consent
- acute illness (eg appendicitis, medical-surgical requiring hospitalization intervention and follow-up)
- In our study provides no substitute for patients who have completed or prematurely abandoned the study. It is contemplated an analysis by intention to treat and the percentage of losses for each treatment group will be collected, clarifying the reason why the study was abandoned.

10. Methodology: Outcomes and variables

a) Variables / Main outcome measure

b) Variables / secondary endpoints measured

b) frequency measurements,

c) Criteria for success and failure, and if necessary

d) Strategy statistical analysis.

Where applicable should be specified and substantiated techniques, equipment and / or instruments to be used in the measurement (this includes mechanical / electronic / cyber special equipment, evaluation forms, questionnaires, matching tables, etc.), indicating the validity criteria , reproducibility and quality controls that are the same.

main outcome variable:

Effect of supplementation of fructans Tequilana Weber blue agave in increasing at least one complete evacuation from basal spontaneous.

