spontaneous evacuation It is defined as an evacuation in the absence of use of laxatives, suppositories or enemas and complete evacuation is defined as spontaneous evacuation to that sensation of incomplete emptying of the rectal ampulla.

secondary measured variables:

- I. Effect of supplementation of fructan Weber blue agave Tequilana in the form of bowel movements, assessed by the Bristol scale. It is defined as a change in the form of evacuations when presenting a change in the classification of Bristol, more than 50% according to the daily evacuations taking the average of the evacuations submitted within 15 days.

- II. Effect of supplementation of fructan Weber blue agave Tequilana in the frequency of bowel movements. It shall be defined as responder presenting increased 50% in stool frequency compared with baseline, according to the daily bowel movements taking the average of evacuations presented at 15 days.
- III. Evaluate the impact of the concentration of short-chain fatty acid, particularly butyrate, in the feces of subjects before and after addition of fructans Tequilana Weber blue agave. The butyrate concentration was determined by method of gas chromatography and the increase will be assessed in millimoles per liter.
- IV. Evaluate the impact of supplementation fructans Weber blue agave Tequilana the microbiota by determining edges present in feces of the subjects before and after the supplementation fructan derivatives fiber; which are:
 - 1) **Actinobacterias** (Bifidobacteriales)
 - 2) **Bacteroidetes** (Prevotella, Paraprevotela, Ruminococcaeaceae, Faecalibacterium)
 - 3) **Firmicutes** (Veillonella, Anaerostipes, lactobacilli Clostridiales, Enterococcus)
 - 4) **Proteobacteria** (Bilophila, Escherichia).
 - 5) **Euryarchaeota** (Methanobacteriales)
- V. To evaluate the impact of serum glucose concentration and HbA1c fasting serum of subjects before and after addition of fructans Tequilana Weber blue agave. HbA1c concentration is determined as it is intended to monitor the impact of fiber on glucose throughout the duration of the study (2 months) and in order to avoid the variability that fasting glucose.

Gas Chromatography: (determination of short-chain fatty acid AGCC)

AGCC for determining ion detector flame will be used. The following steps are performed:

1. ethylbutyrate - 1 g of faeces which is added 50 uL of 2 homogenizará.
2. 1 mL of hydrochloric acid was be added.

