Sequencing and analysis of the amplified fragments is by fluorescent sequencing equipment terminator 3130 / genetic analyzer (Applied Biosystems).

The PCR products were sequenced and analyzed and will be submitted to GenBank for species identification.

Extracting bacterial DNA and quantitation of bacterial species used to demonstrate the prebiotic effect of agave fiber, since selective growth of the population of bifidobacteria and lactobacilli and occurrence of short-chain fatty acid in stool is expected.

Thus in addition to the functional properties and their effects on constipation, you may check the prebiotic effect of agave fructans.

Data analysis:

a) Statistical analysis plan

The data obtained will be analyzed with SPSS version 24. For continuous variables the results are presented in mean ± standard deviation when the variables are normally distributed or medians and percentiles otherwise and as frequency and percentages when they were categorical. For basal and subsequent comparison to the intra intervention groups, Student's t-test for paired samples (variables with normal distribution) or the Mann-Whitney U (variables without normal distribution) is used in the case of continuous variables and X² or the McNemar test in the case of categorical variables. For comparison between groups ANOVA (variables with normal distribution) or Kruskal-Wallis (non-normal distribution variables) used for continuous variables and the same percentage of change obtained when the variables are continuous.

Also an analysis of covariance (ANCOVA) was performed to control variables that might have an effect on the response variables.

b) Non-inferiority study

There are multiple fibers on the market that are promoted as beneficial supplement to patients with constipation; Despite this, there is insufficient scientific evidence from randomized controlled trials to support its use. Psyllium psyllium, is the first-line treatment used for such functional bowel disorder; fructans tequilana Weber blue variety are soluble fibers which are rich fructooligosacáridos role in prebiotic substance with the which is associated with a number of health benefits including intestinal health; therefore, as an alternative treatment in patients with constipation using these fructans it is raised to generate clinical evidence and demonstrate the therapeutic potential similar to plantago psyllium.

c) Sample size

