Discomforts generated by the study:

Discomfort from the study are related to the puncture for blood collection (3). It is anticipated that the fiber, when containing fructans, generate a fermentation process with flatulence and bloating. However, reports of studies using the fiber, have shown that this effect is transient lasting 2 weeks.

Risks:

Regulation of the General Law of Health in Research for Health, said that obtaining biological samples represents a minimal risk in the investigation. The risks of blood sampling are: possibility of slight bleeding or bruising at the puncture site, dizziness or fainting and rarely arterial puncture may occur. Personnel draw the blood sample is trained for this, which will minimize the risks of complications.

If there are complications will be referred directly to your treating physician. It is anticipated in the informed consent we do not have resources in case complications arise.

Benefits:

Administration fiber, it has shown to be healthy and beneficial for the treatment of functional constipation. Such supplementation, is the first line treatment of functional constipation. Patients entering this study will benefit from fiber start treatment within the diagnostic and therapeutic approach constipation.

Moreover, thanks to the participation of volunteers, your community can benefit significantly by finding new ways to address this medical complication.

Rescue measures:

If the patient has no spontaneous evacuation after 72h will prompt the patient to contact the research team, for instructions such as laxatives previously prescribed by your physician. If distended or flatulence, using anti detergents (simethicone) that is effective to treat this condition is allowed. For present colic, it can be used a conventional antispasmodic. each of the side effects will be recorded as well as the need for therapies rescues specified above.

13. Schedule of activities

The letter updating the research project is attached. (Annex 1)

Activities	2018												2019												2020											
	J	F	M	A	M	J	J	A	S	O	N	D	J	F	M	A	M	J	J	A	S	O	N	D	J	F	M	A	M	J	J	A	S	O	N	D
Moith																																				
Research topic selection	■																																			
Search and review of the biography	■	■	■	■	■	■	■	■	■	■	■	■	■	■	■	■	■	■	■	■	■	■	■													
Protocol writing	■	■																																		
Review of the protocol by the research group			■	■																																

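### The stool-frequency responder rule (secondary variable II) does not exclude evacuations after rescue laxatives, so laxative-induced stools can count as response to the fibre

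*Combined protocol and SAP*

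**What the plan says.** Section 10 (Outcomes and variables) bases the main outcome on "increasing at least one complete evacuation from basal spontaneous" and then gives the definition: "spontaneous evacuation It is defined as an evacuation in the absence of use of laxatives, suppositories or enemas". Secondary variable II follows in the same section. It calls a patient a "responder presenting increased 50% in stool frequency compared with baseline, according to the daily bowel movements", averaged over 15 days, and does not mention spontaneous evacuations or laxatives.

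Section 12 (Rescue measures) covers the patient who "has no spontaneous evacuation after 72h will prompt the patient to contact the research team, for instructions such as laxatives previously prescribed by your physician". It adds that "each of the side effects will be recorded as well as the need for therapies rescues specified above".

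Section 8 (Study design) says of the period before treatment that "the previous use of fiber supplements and laxatives, which must be suspended at Least 2 months prior to randomization".

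The data analysis section, parts a) to f), contains no rule for stools that follow rescue. Part a) plans paired tests "For basal and subsequent comparison to the intra intervention groups". For comparisons between groups it names tests for continuous variables only.

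**The concern.** Secondary II is meant to show what the fibre does to stool frequency. A patient whose fibre fails reaches 72 h without a spontaneous evacuation, may take a laxative, and then passes a stool that enters the diary. Nothing in the responder rule removes that stool. The baseline is planned without laxatives, so the on-treatment count can contain something that the baseline count does not, and failure on the fibre can move a patient toward response.

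Two results are exposed: the responder rate in each arm, and the within-arm change in stool frequency that part a) would test. Two arms with the same true effect could also look different because one used more rescue.

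A related gap is that the definition of spontaneous gives no time window after laxative use. Two analysts could classify the same stool differently, and this also affects the main outcome.

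**Working it through.** **What the plan gives.** It states no responder rate, rescue rate or baseline frequency for secondary II, so there is no figure to reproduce. Usable inputs are the 50% threshold and 15-day window (section 10), the 72 h trigger (section 12) and 15 patients per arm (section 8, 60/4).

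**Threshold arithmetic.** At one stool per week the baseline count is 15/7 = 2.14 in 15 days. The threshold is 1.5 × 2.14 = 3.21, so 4 stools make a responder. A 72 h trigger allows up to 15/3 = 5 rescue episodes in 15 days. With one stool per episode, a patient with no spontaneous stool at all could qualify.

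**Illustrative model.** Assumptions not in the documents: baseline of 1, 1.5, 2 or 4 stools per week; a share p of gaps over 3 days is rescued; the rescued stool comes at 3.5 days. Intervals between stools follow gamma distributions with shape 1 (random), 2 or 4 (regular). Patients with a baseline count of 0 are left out. A responder has a count of at least 1.5 times baseline.

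**Check on the mean (random intervals).** With m = 7/frequency and P = exp(−3/m), the new mean interval is m − p[P(3 + m) − 3.5P] = m − pP(m − 0.5).
- 1/week, p = 0.3: m = 7, P = 0.651; 7 − 0.3 × 0.651 × 6.5 = 5.73; frequency rises by 7/5.73 − 1 = 22%.
- 2/week: m = 3.5, P = 0.424; 3.5 − 0.3 × 0.424 × 3 = 3.12; rise 12%.
- 4/week: m = 1.75, P = 0.180; 1.75 − 0.3 × 0.180 × 1.25 = 1.68; rise 4%.

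**Responders in an arm with no true effect, all stools counted** (simulation; ranges run over the three shapes):

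| Baseline | No rescue | 30% uptake, treatment only | Gain, points | 30% uptake, both windows |
|---|---|---|---|---|
| 1/week | about 31% | 40–42% | 9–11 | 30–31% |
| 2/week | 17–30% | 20–36% | 3–6 | 15–28% |
| 4/week | 7–23% | 7–25% | 0–2 | not used here |

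A second model (Poisson stools, a daily chance of rescue after three stool-free days) shows the same pattern. At 2/week, 30% respond on spontaneous stools, against 35% to 60% on all stools as the daily chance goes from 0.1 to 1. With a chance of 0.5 at baseline too, the rate falls to about 17%.

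**Between arms.** The gain column is also the spurious difference between two no-effect arms with 30% and 0 uptake. For an arm with a true 50% rise against a no-effect arm at 1/week, the difference is 18–29 points without rescue and 17–24 with 30% uptake in both. It reverses to between −25 and −15 only at an extreme split (every gap rescued in the no-effect arm, 30% in the other). For scale, with 15 per arm the standard error of a difference near 50% is √(2 × 0.25/15) = 0.183, about 18 points.

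**After the fix.** Counting spontaneous stools only, two no-effect arms at 30% and 0 uptake differ by 0 to 8 points at 1/week, now against the arm with more rescue. With regular intervals the error is about 6 points at 1.5/week and 5 at 2/week, compared with 5 and 3 in the other direction when all stools count. With random intervals it is 1 to 2 points, compared with 5 to 8 when all stools count.

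**The case against.** *The baseline may not be rescue-free.* Section 12 does not confine rescue to the treatment period, and patients keep the evacuation diary before randomization while off laxatives. This stands: equal use in both windows removes the inflation, so its direction is conditional.

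*The definition may have been meant for the whole section.* It stands directly above the secondary variables in a translated text. That is possible, but secondary II does not invoke it, and the ambiguity itself needs resolving.

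*The diary form may already record laxatives and dates.* It is in annexes that were not supplied, so nothing can be said against the form. An analysis rule would still be missing.

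*No planned test of the responder rate is affected.* This stands. A responder is already a change from baseline and has no baseline state, so the paired tests in part a) apply to stool frequency, not to the responder rate. A reader might infer that these tests of responder rates are biased; the documents plan none.

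*The sizes are assumed and mostly small.* They rest on assumed uptake and baseline frequency. Rescue requires contact with the team, chronic users of stimulant laxatives are excluded, and patients without low frequency can enrol because two of six Rome III symptoms suffice. At two or more stools per week the gain is well below the standard error. That limits the grade, but a systematic error does not average out.

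*The fix can swap the sign of the error.* This stands for regular intervals, as shown above. It is why rescue use has to be reported with the result.

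**Conclusion.** The concern holds in conditional form. As written, secondary II lets stools that follow a rescue laxative count as response to the fibre, and no part of the analysis plan removes them. If the baseline is laxative-free, as section 8 intends, responder rates and within-arm changes in stool frequency can be inflated. At an assumed 30% uptake on treatment only, the gain is about 9–11 points at 1/week, 3–6 at 2/week and 0–2 at 4/week. If rescue is used equally at baseline, there is no inflation.

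A reader might go further and conclude that the comparison of agave with psyllium is biased in a known direction. The documents do not support that. They give no rescue use by arm, so the difference may be unchanged, narrowed, widened or, at extreme splits, reversed. Between-arm differences in responder rates are also descriptive, because part a) names between-group tests only for continuous variables. Nor does the main outcome share the omission: it is limited to spontaneous evacuations, and only the missing time window touches it.

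This is a secondary variable and the remedy is cheap. The change should be made before analysis, but it does not put the trial's main result in doubt.

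**What to change.** - In secondary II, count only evacuations that meet the plan's own definition of spontaneous, in both the baseline and the treatment windows.
- State one fixed time window after use of a laxative, suppository or enema within which a stool is not spontaneous, and use it for the main outcome too.
- Record the date of rescue use, if the diary form does not already do so, so that it can be matched to the evacuation diary.
- Report rescue use by arm and by period beside the responder rates.

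The rescue rule itself is unchanged.

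The cost is a few sentences in the outcome definitions and one matching step in the data. Responder rates will be somewhat lower, because rescue displaces some stools that would have been spontaneous. In an arm with a true 50% rise and 30% uptake at 2/week, the simulated rate goes from 53–55% on all stools to 48–51% on spontaneous stools. A residual error of 0 to about 8 points against the arm with more rescue remains at 30% and 0 uptake, largest with regular intervals. The responder rates should therefore not be read without the table of rescue use.

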The initial treatment of Patients with Functional constipation is based on fiber. There are multiple fiber products in the market, which are Promoted as a supplement for constipation without any scientific evidence to support ITS use. Furthermore, the tolerability of These compounds limits long-term Their use in esta patient population. Scientific evidence is required to support the effectiveness in the use of These fiber supplements in Patients With functional constipation.

6. Justification

There are multiple fibers are in the market That Promoted as a beneficial supplement for Patients With constipation, DESPITE esta, there is not enough scientific evidence derived from randomized and controlled studies to support ITS use. THEREFORE, it is Necessary to Provide evidence to support the use of blue agave fructans Tequilana Weber in Patients With functional constipation.

7A. hypothesis

Defined as a verifiable statement About the relationship Between a variable-dependent and an independent variable. (Remember That the concepts of "null hypothesis", "alternate hypothesis" are related to the statistical analysis So They Should not be included in this item)

General Hypothesis:

Plantago Psyllium When Compared With, the blue agave fructans Weber Tequilana have a like effect or are more effective in Improving functional constipation in adult patients.

Objectives

PRIMARY

1. To Evaluate the efficacy of the blue agave fructans Tequilana Weber in Patients With functional constipation.

SECONDARY

1. To compare the efficacy and tolerability of 5 and 10g doses of blue agave fructans Tequilana Weber in Patients With functional constipation.
2. To Evaluate the impact of the consumption of blue agave fructans Tequilana Weber on the quality of life of the subjects WHO ingest it by Applying the quality of life questionnaire SF-36.
3. To determine the impact of the blue agave fructans of Weber Tequilana intake in the fasting glucose, glycosylated hemoglobin A1c and the lipid profile (metabolic profile) of the subjects WHO ingest it.
4. To Evaluate the presence of short chain fatty acids (butyrate) before vs after the treatment with blue agave fructans Tequilana Weber.
5. To determine the impact of the ingestion of blue agave fructans Tequilana Weber in the microbiota before vs after ingestion.
6. Evaluate to the tolerance to the ingestion of blue agave fructans Weber Tequilana through the use of breath test.

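### The plan does not say that conclusions about agave rest on the randomised comparisons, and its within-arm tests, which cannot isolate agave, are not marked as descriptive

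*Combined protocol and SAP*

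**What the plan says.** **Objectives.** The primary objective is "To Evaluate the efficacy of the blue agave fructans Tequilana Weber in Patients With functional constipation", with no comparator. Secondary objective 4 is "To Evaluate the presence of short chain fatty acids (butyrate) before vs after the treatment with blue agave fructans Tequilana Weber". Objective 5 looks for an effect "in the microbiota before vs after ingestion", and objective 7 treats gastrointestinal transit in the same way. In section 10, the main outcome is the effect of agave "in increasing at least one complete evacuation from basal spontaneous", and secondary variables III to V (butyrate, microbiota, glucose and HbA1c) are also before and after.

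**Analysis.** Data analysis, a) lists the within-arm tests first: "For basal and subsequent comparison to the intra intervention groups, Student's t-test for paired samples", or Mann-Whitney U if not normal. Chi-square or McNemar for categorical variables appear in the same sentence. Between-group tests follow: ANOVA or Kruskal-Wallis for continuous variables, including percentage change, and ANCOVA with unnamed covariates. Data analysis, d) applies p < 0.05 to every variable. Nothing marks the within-arm tests as descriptive.

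**Comparative elements.** The general hypothesis (section 7A) is that "Plantago Psyllium When Compared With, the blue agave fructans Weber Tequilana have a like effect or are more effective" in improving constipation. Data analysis, b) and f) describe a non-inferiority aim against psyllium.

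**Design.** Section 8 randomises 60 patients, 15 per arm, to psyllium 15 g, agave 5 g, agave 10 g, or agave 5 g plus 10 g excipient. No arm is free of fibre. On the run-in, section 8 says "The amount of daily fiber intake will be standardized and a diary will be Given to Evaluate Said intake". Previous laxatives and fibre supplements are those "which must be suspended at Least 2 months prior to randomization". Nutritionist review continues at Visits 3, 4 and 5.

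**The concern.** A test of change within an agave arm asks whether patients improved. It does not ask whether agave improved them. Three things other than the product can move the outcome after baseline:

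- dietary review that continues during treatment;
- regression to the mean, because patients enter while meeting Rome III criteria;
- the natural course of the condition.

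With no fibre-free arm, nothing in the trial measures how much change these would produce.

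The randomised contrasts (agave against psyllium, one agave arm against another) balance these influences on average. The plan does not say that they carry the conclusions. As written, a report could answer the primary objective, or state that agave raises butyrate, alters the microbiota or speeds transit, from a within-arm p-value that makes no use of the randomisation. The protocol's own justification for the trial is the shortage of randomised, controlled evidence.

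**Working it through.** **1. Which comparison each claim leads to**

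| Item | Comparator in its wording | Test the plan clearly supplies |
|---|---|---|
| General hypothesis, 7A | psyllium | between-group tests, continuous variables only |
| Primary objective | none | not stated |
| Main outcome (gain of at least one complete spontaneous evacuation) | own baseline | categorical tests appear only in the within-arm sentence |
| Objectives 4, 5, 7 | own baseline | within-arm; between-group if continuous |
| Objective 1 (5 g and 10 g) | the other dose | between-group tests, continuous variables only |

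The main outcome reads most naturally as a threshold, so each patient is a responder or not. The between-group sentence names no test for that kind of variable.

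**2. The plan's own figure**

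Data analysis, c) gives n = λ/Δ = 10.91/1 = 10.91, about 11 per arm, then 15 after a 20% allowance for loss, and 4 × 15 = 60. The noncentrality of a chi-square with 3 degrees of freedom at α = 0.05 and 80% power is 10.90, against 10.91 stated. Dividing by 0.8 gives 11/0.8 = 13.75, or 14, close to the 15 chosen. So λ belongs to a four-group comparison, and the sample size was not built on a within-arm test. The section gives no non-inferiority margin.

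**3. Within-arm test when agave has no effect of its own (illustration)**

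Inputs: n = 15 per arm (section 8), or 15 × 0.8 = 12 completers after the planned 20% loss. α = 0.05 is from the plan; two-sided is assumed, because the plan does not say. The non-product shift d, in SDs of the change, is an assumption: the documents give neither an SD of change nor a non-specific response.

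The probability of significance is P(|T| > t), with T noncentral t, n − 1 degrees of freedom and noncentrality d√n. For n = 15, √15 = 3.873, so d = 0.5 gives 1.936.

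| d | One arm, n = 15 | One arm, n = 12 | At least one of three agave arms, n = 15 |
|---|---|---|---|
| 0 | 5% | 5% | 14% |
| 0.25 | 15% | 12% | 38% |
| 0.5 | 44% | 35% | 82% |
| 0.75 | 77% | 66% | 99% |
| 1.0 | 95% | 88% | about 100% |

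The last column is 1 − (1 − p)³. At d = 0.5 it is 1 − 0.562³ = 0.82.

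**4. What the randomised contrasts can deliver**

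For two arms of 15 the noncentrality is d√(15/2) = 2.739d with 28 degrees of freedom. Power for a true difference of 0.5 / 0.75 / 1.0 SD is 26% / 51% / 75%. For 80% power, n per arm is about 2(1.960 + 0.842)²/d² = 15.70/d², which is 63 / 28 / 16 before loss.

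**The case against.** The strongest reply is that the trial is already comparative. The hypothesis names psyllium, the analysis plan has a non-inferiority section, and ANOVA, Kruskal-Wallis and ANCOVA are planned between groups. An active comparator that the protocol calls first-line is a legitimate choice, and before-after tests can be read as supporting description. This largely stands. A reader might infer that every efficacy conclusion would be confounded; the documents do not support that, because non-product effects balance in the randomised contrasts. Nor does any section say that a significant within-arm test establishes efficacy. What remains is that the plan does not say which analysis carries the conclusion.

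A reader might also infer that diet standardisation and diary keeping inflate the change. Both begin before Visit 3, so whatever effect they have had by then is in the stool, blood and questionnaire baselines. Only later or continuing effects are at issue.

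Recovery after laxative withdrawal is a further tempting reading. It is speculative: withdrawal is at least 2 months before randomisation, chronic stimulant-laxative users are excluded, and laxative-assisted evacuations do not count as spontaneous. The requirement of symptoms for more than 6 months also limits regression to the mean, without removing it.

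Finally, the percentages are a power curve at assumed shifts for a continuous variable. They are not an estimate of this trial's error rate and do not apply directly to a yes/no main outcome.

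**Conclusion.** The point holds as one of priority and wording. The primary objective has no comparator, objectives 4, 5 and 7 are before-versus-after, all arms take fibre, and the within-arm tests are held to p < 0.05 with no descriptive label. Following the plan as written could therefore credit non-product change to agave.

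The possible size depends wholly on an assumed shift: 15% to 95% significance per agave arm for 0.25 to 1.0 SD with 15 patients, against a nominal 5%. The assumptions are a two-sided test, a normally distributed change and no effect of agave itself.

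The psyllium comparison does not supply an absolute effect. Equal non-specific gains in all arms would look like similarity, and without a non-inferiority margin a non-significant difference does not show similarity either.

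**What to change.** 1. Align the primary objective with the general hypothesis: efficacy of agave relative to psyllium.
2. State that conclusions on efficacy, butyrate, microbiota, metabolic profile and transit rest on randomised between-arm comparisons of change. Each measure should use its own pre-randomisation baseline: Visit 3 for stool and blood, Visit 2 (compared with Visit 4) for SmartPill, and the pre-treatment diary for evacuations.
3. Name a between-arm comparison of proportions for the main outcome.
4. Label within-arm before-after tests as descriptive, with no claim attached.
5. State in the report that an absolute effect of agave is not estimated without a fibre-free arm, and that a non-significant difference from psyllium does not by itself show similarity, because no margin is given.

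This changes wording only and needs no new patients or data. The sponsor gives up before-after efficacy claims and relies on contrasts with limited power at 15 per arm, about 26% / 51% / 75% for true differences of 0.5 / 0.75 / 1.0 SD.
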